**Estimated Detectable Effect Sizes for the Primary Outcomes (N = 250)** 

 As described in the text, under the Hochberg procedure the statistical power for each of the two primary outcomes depends in part on the effect size for the other outcome. Thus, the minimum detectable effect on the LVmass-Mortality composite is evaluated assuming treatment effects on the change in the PHC of either 0, 2.28 (corresponding to 25% of the estimated standard deviation of the change in the PHC score after covariate adjustment), or 4.56 units (corresponding to 50% of one standard deviation). Similarly, the treatment effects on the PHC-Mortality composite are evaluated assuming effects of either 0, 6 (25% of 1 SD) or 12 g on the change in LVmass. The simulation results indicate the above calculations are accurate if the correlation between the change in LVmass and the change in the PHC score is between 0 and +0.5.

Assumed SD of 1 Yr **Outcome Variable** 80% power 90% power Change PHC (points) 8.310 3.31 3.83 LV mass (g) 24.009.6 11.1 Average Albumin (g/dL) 0.296 0.12 0.14 Average serum phosphorus (mg/dL) 1.636 0.66 0.77 Beck Depression Inventory  $(1 \text{ SD})^2$ 0.40 0.46 Trail Making Test B  $(1 \text{ SD})^2$ 0.40 0.46

Table 15bEstimated Detectable Effect Sizes for the Main Secondary Outcomes  $(N = 250)^1$ 

 Treatment effect tested at alpha = 0.05 using a 2-sided test. The estimated minimum detectable reduction in rate of non-access hospitalization or death is 39% and 45% at 80% and 90% power, respectively.

 Detectable treatment effects expressed per 1 standard deviation of the changes in the Beck Depression Inventory and Trail Making Test B because pilot data on 1-year changes in these outcomes in dialysis patients is not available.

account information provided by the 4 month measurements for patients with missing data at 12 months, and in this respect are slightly conservative.

Assuming event rates in the control group of this trial are similar to those observed in the HEMO Study, that the relationship between non-access hospitalizations and death events are similar between the two trials, and that the loss-to-follow-up rates are also similar, the estimated minimum detectable reduction in rate of non-access hospitalization or death is 39% and 45% at 80% and 90% power, respectively.

#### **10.** Safety and Monitoring

#### 10.1 Data Safety and Monitoring Board (DSMB)

The External Advisory Committee/Data Safety and Monitoring Board (DSMB) will meet regularly to review the safety of the participants during the course of the study. In addition, the DSMB will monitor the operational progress of the trial and evaluate interim analyses of treatment efficacy performed by the Data Coordinating Center.

The specific activities of the DSMB will vary during the course of the trial. Prior to the start of the trial, the DSMB will review and approve the protocol and template informed consent form. During the Vanguard phase in the trial's first year, the DSMB will review quarterly reports summarizing the operational conduct of the study, including analyses of recruitment, retention, adherence, and quality control. The quarterly reports will include specific assessments of the success of the trial in meeting the pre-designated benchmarks for the Vanguard phase. The DSMB will also review quarterly

tabulations of stop points, action items, and adverse events. The DSMB will meet by teleconference after receiving the second quarterly report, and more often if necessary, to verify the safety of the trials and provide feedback regarding the operational issues.

After the completion of the Vanguard phase, the DSMB will meet in person to determine whether the trial should proceed to completion based on the extent to which the benchmarks established for the Vanguard phase are met. Depending on the success of the Daily HD trial and its parallel Nocturnal HD trial in meeting their operational goals, the DSMB may recommend a revision of the target sample sizes and reallocation of resources between the two trials.

After the Vanguard Phase, subsequent interim reports will be provided to the DSMB at months 15, 21, 27, and 33. These reports will include summaries of the operational progress of the trial and patient safety, as well as interim analyses of the effects of the treatment interventions on the primary and main secondary endpoints at 4 and 12 months follow-up. The DSMB will meet by teleconference following distribution of the month 15 and month 27 reports, and will hold face-to-face meetings following the month 21 and month 33 reports. If necessary, additional teleconferences and face-to-face meetings will be scheduled.

### 10.2 Definition and Reporting Safety-Related Adverse Events

A Standards of Care/Clinical Management Committee will oversee that standards of care are being met (see Section 3.4.2). A blinded Outcomes Committee will monitor and investigate adverse events that will be reported to the DSMB. The following adverse events will be reported monthly by the DCC to the Outcome Committee (see Section 7) who will investigate them and complete an Assessment of their seriousness and relatedness to the randomized therapy. The frequency of these adverse events and detailed assessments will be reviewed by the DSMB quarterly. The adverse events to be handled in this way are:

i) all deaths which occur during the hemodialysis session itself

Safety analyses presented at annual DSMB meetings will include summary reports of frequency and differences between treatment groups for each of the following:

- i) deaths
- ii) hospitalizations
- iii) vascular access events (interventions and failures)
- iv) adherence rates

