# 6.3 Definitions, Monitoring and Reporting of Patient Events

# 6.3.1 Outcome Classification Committee

An Outcome Classification Committee will be composed of the Clinical Center Principal Investigators, who will review all deaths and 100 hospitalizations to verify cause of death or hospitalization (see below). The members of the Outcome Committee will be trained by the Data Coordinating Center in order to provide a standard classification system for patient deaths and hospitalizations. The Data Coordinating Center will remove any information that can identify the randomization status of the patient being reviewed so that members of the Outcome Committee will be blinded to the patient's treatment allocation.

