### 7.2 Action Items

# 7.2 Action Items

The DCC will report and the Outcome Committee will review (in conjunction with Kinetic Modeling Committee) any patient who has persistent underdialysis (i.e., for conventional group, not meeting eKt/V of 1.10 per session for 2 or 3 consecutive measurements; for daily and nocturnal group, not meeting a std Kt/V of 2.0 for 3 consecutive measurements)

a) DCC will report and the Recruitment and Adherence Committee will review any patient who has persistent nonadherence to therapy. Persistent nonadherence to be defined and monitored with appropriate action by adherence committee (in conjunction with Kinetic Modeling Committee).

- b) DCC will report and the Standards of Care/Clinical Management Committee will review any patient who has persistent hypophosphatemia (serum phosphate level less than the lower limit of the normal range) on 2 or 3 consecutive monthly measurements
- c) The Central HRQL Survey Center will report within 24 hours to the research coordinator or treating nephrologist any patient who has potentially life-threatening findings on tests done exclusively for the purpose of the study. These findings will also be reported to the DCC who will report these findings in a timely manner to the study center when received by the database. These findings may include, but are not limited to:
  - i) scores above a certain threshold that indicates depression on the Beck Depression Inventory
  - ii) answers 2 or 3 on question #9 of the Beck Depression Inventory ("would you kill yourself")
- d) The Central Holter Core will transmit a report to the Data Coordinating Center for any patient who has potentially clinically relevant findings on tests done exclusively for the purpose of the study. The DCC will report these findings in a timely manner to the study center when received by the database. These findings may include, but are not limited to: arrhythmias due to ventricular tachycardias, torsades de pointes, AV blocks 2b and 3, sinus arrest / SA blocks 3, and atrial fibrillation.

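### The blinded Outcome Committee reviews arm-specific underdialysis reports (7.2), and its relatedness assessment (10.2) covers only in-session deaths and asks about a regimen it cannot know

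*Protocol*

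**What the plan says.** Section 6.3.1 sets up the committee: "An Outcome Classification Committee will be composed of the Clinical Center Principal Investigators". They review all deaths and a sample of hospitalizations. To keep them blinded, "The Data Coordinating Center will remove any information that can identify the randomization status of the patient being reviewed".

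Section 10.2 repeats the requirement: "A blinded Outcomes Committee will monitor and investigate adverse events that will be reported to the DSMB". The Data Coordinating Center (DCC) passes events to the committee monthly, with a cross-reference to Section 7. The committee's task is described by "who will investigate them and complete an Assessment of their seriousness and relatedness to the randomized therapy", and the events handled this way are a single item: "all deaths which occur during the hemodialysis session itself".

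Section 7.2 gives the same committee another duty: "The DCC will report and the Outcome Committee will review (in conjunction with Kinetic Modeling Committee) any patient who has persistent underdialysis". The trigger depends on the arm. One part reads "for conventional group, not meeting eKt/V of 1.10 per session for 2 or 3 consecutive measurements". For the daily arm it is a std Kt/V below 2.0 on three consecutive measurements.

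For other events, Section 6.3.3 has one committee member verify the cause of every death. Section 6.3.2 has the site answer expectedness and relatedness questions for each hospitalization, while the committee rechecks only cardiovascular and access status in a sample. Under 6.3.3, a hospitalization that ends in death yields the same data as any other hospitalization.

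**The concern.** Two instructions do not fit together. The committee must not know the allocation, yet it receives reports whose defining measure differs between arms. A member who has reviewed such a report knows the arm of that patient and may later be asked to code that patient's death or hospitalization blind. The committee's death code is the one used in analysis. Its access and cardiovascular category is final for the 52 hospitalizations reviewed early in the trial. Access status separates the events that count in the main secondary outcome of non-access hospitalization or death from those that do not.

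The relatedness assessment has two further weaknesses. It reaches only deaths that happen on dialysis, although every death packet already goes to the committee. And the question as worded concerns the randomized therapy. Both arms receive hemodialysis, so a blinded member can say whether a death was connected with dialysis or the access, but not whether six sessions a week rather than three contributed. Safety, with a focus on vascular access events and participant burden, is a stated trial objective (Section 2.1).

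**Working it through.** The protocol states no count of in-session deaths, so there is no figure to reproduce. The main check is a comparison of sections.

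**Blinding**

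| Section | Instruction | Consequence |
|---|---|---|
| 6.3.1, 10.2 | Committee is blinded; the DCC strips allocation from the material | Members should not know the arm |
| 7.2 | Same committee reviews underdialysis, by eKt/V 1.10 (conventional) or std Kt/V 2.0 (daily) | The criterion identifies the arm |
| 6.3.2, 6.3.3 | Same committee codes deaths and sampled hospitalizations | A flagged patient may come back for blind coding |

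**Who judges relatedness of a death**

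| Death occurs | Site | Committee |
|---|---|---|
| During a session | As below, by place of death | Yes (10.2) |
| In hospital, outside a session | Yes, via the hospitalization data (6.3.2, 6.3.3) | Cause only |
| Outside hospital and outside a session | Narrative and presumed cause; no relatedness question stated | Cause only |

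The last row is the gap.

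**Scale (illustration)**

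Inputs: 250 patients, so 125 per arm (2.4); 12%/yr control mortality, exponential (9.11); a hypothesized 20% reduction (9.11); median weekly treatment time of 10.5 h conventional and 14.2 h daily (Executive Summary). Assumed, because the protocol gives no value: the in-session hazard is k times the hazard at other hours, with k from 1 to 3.

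Expected deaths in 12 months:
- Conventional: 125 × (1 − exp(−0.12)) = 14.1
- Daily: 125 × (1 − exp(−0.096)) = 11.4
- Total: about 25.6. Allowing for 4%/yr transplantation gives 25.1. With no mortality effect the total is 27.7 to 28.3.

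Share of the week on dialysis, s: 10.5/168 = 0.0625 and 14.2/168 = 0.0845.

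In-session share of deaths = k·s / (1 − s + k·s).

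| k | Conventional | Daily | Total of 25.6 |
|---|---|---|---|
| 1 | 14.1 × 0.0625 = 0.88 | 11.4 × 0.0845 = 0.97 | 1.9 (7%) |
| 3 | 14.1 × 0.167 = 2.4 | 11.4 × 0.217 = 2.5 | 4.8 (19%) |

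At k = 2 the total is 3.4. So 25.6 − 4.8 = 20.8 to 25.6 − 1.9 = 23.7 deaths, about 81% to 93%, would get no committee relatedness judgment.

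**The case against.** The strongest reply is that most of the safety review lies elsewhere and is intact. Sites, which know the treatment, answer relatedness questions for every hospitalization, including those that end in death. All deaths get a cause review. The DSMB receives adverse event tabulations (10.1), access complication rates per arm (6.3.4), and arm comparisons of deaths, hospitalizations and access events (10.2). In a randomized trial that comparison is the main causal evidence. This stands. A reader might infer that causality review is empty; the documents do not support that.

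A reader might also infer that the committee's blind is lost in general. That too goes beyond the text. Only flagged patients are affected, and only if a member can link the report to a later packet. Section 7.2 does not say how patients are identified in these reports. Dose warnings to sites carry a study ID number (3.1.4), but no section says the same of reports to the committee. Flags may also be few. Table 3 projects a 5th percentile of eKt/V of 1.12 in the conventional arm, just above the 1.10 trigger, and of std Kt/V of 3.32 in the daily arm, far above 2.0. These are simulated values, and patients may enter with a baseline mean eKt/V as low as 1.00, so the number flagged is unknown rather than zero.

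The effect on outcomes is limited. Sites classify all hospitalizations, and the committee rechecks 52 and then 12 a year. Both co-primary composites use all-cause mortality, and the main secondary event outcome counts every death, so cause coding changes none of these.

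Two other inferences fail. In-session deaths are not expected to be unbalanced between arms (0.88 against 0.97 at k = 1). And nothing in the documents says where access-related deaths mostly occur.

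None of this removes the conflict between 7.2 and the blinding rule, or the missing relatedness judgment for deaths outside both hospital and session.

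**Conclusion.** The point holds in a limited form. Section 7.2 gives a committee that must be blinded reports that reveal the arm, so Sections 6.3.1, 7.2 and 10.2 need to be reconciled for flagged patients. Section 10.2 restricts the committee's seriousness and relatedness assessment to in-session deaths, leaving deaths outside both a session and a hospital with no stated relatedness judgment. It also asks a blinded committee about the assigned regimen, when it can judge only dialysis itself or the access.

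On the illustrative figures the restriction covers about 2 to 5 of about 26 deaths. That range rests on the protocol's mortality assumptions and on an assumed in-session hazard. The number of patients whose blind is at risk cannot be derived from the protocol. The weakness concerns safety review and the blind coding of sampled events, not the primary analysis.

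**What to change.** 1. Section 7.2: send underdialysis reports to the Kinetic Modeling Committee, already named there, or to another committee that does not classify outcomes blind. The review itself stays, and the thresholds are not at issue here.
2. Section 10.2: replace in-session deaths with all deaths, and record whether the death fell in a session as an attribute. Have the committee, still blinded, rate relatedness to dialysis or vascular access instead of to the randomized therapy.
3. Leave attribution to the randomized regimen to the DSMB, which sees results by arm. Do not show assignments to the committee for this purpose: its members are the Clinical Center Principal Investigators, and rating every death with the assignment visible would reveal mortality by arm to recruiting investigators during the trial.

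The cost is protocol wording and one extra form field for roughly 20 or more further deaths, whose packets already reach the committee under 6.3.3. The real downside is that one fewer committee looks at underdialysis, unless another unblinded committee takes the Outcome Committee's place.

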### 10.3 Stopping Rule

A formal stopping rule for efficacy will not be used because none of the intermediate outcomes are judged to be sufficiently definitive to warrant early termination of the trial, and because it is unlikely to be feasible to switch a large proportion of the patients in the conventional arm to the frequent dialysis therapy until after the scheduled termination of the trial. However, to assist the DSMB in interpreting results from multiple looks at the data, the DCC will provide thresholds for statistical significance for each intermediate outcome based on the O'Brien-Fleming rule [O'Brien, 1979].

